## 6.2.3 Treatment Group

The treatment group will receive treatment at the start of the study and an optional touch-up treatment 1 month later. They will be followed for safety and effectiveness for 12 months with the option for a repeat treatment and an additional month of follow-up at Month 12.

### 6.2.3.1 Initial Treatment, Touch-up Treatment, and Follow-up

If the subject is randomized to the treatment group, initial treatment should be performed on the same day as randomization. In addition, vision assessments (Snellen visual acuity, confrontational visual fields, and ocular motility) will be performed before treatment. The EI will not be present during any treatment procedures.

Anesthesia will be administered following the standard practice at each investigational site. The application of ice and topical anesthesia is allowed to reduce injection discomfort. Injectable anesthesia must be limited to the treatment area only. The TI will use aseptic skin preparation and will administer injections to both the right and left treatment area according to the investigational directions for use (IDFU) and [Section 9.1.2](#) of this protocol. The TI will determine the appropriate volume to inject to achieve optimal correction based on clinical experience.

Approximately 30 minutes after treatment, the TI (or designee) will perform vision assessments. The TI will also evaluate treatment characteristics, including injection ease and product moldability, and will record any AEs.

Subjects will receive instructions on how to evaluate the treatment areas, assess the procedural pain on an 11-point scale, and complete the daily safety diary to record the presence or absence and severity of injection site responses (ISRs) starting on the day of treatment and for approximately 30 days after treatment.

Subjects will complete a safety follow-up telephone call 3 days after treatment. If any change to vision is reported during a telephone follow-up or unscheduled phone call, the subject will be asked to come in immediately or will be referred to a retinal specialist for further evaluation. Subjects will return for an office visit 14 days after treatment to undergo [REDACTED] imaging, and the TI (or designee) will perform vision assessments. The subject will not see the blinded EI at the Day 14 visit.

Thirty days after treatment, the subject and the TI will discuss the results of the initial treatment, [REDACTED], [REDACTED], a touch-up may be performed if agreed upon by the subject and TI. The procedures performed after touch-up treatment are the same as those after initial treatment.

For initial treatment and touch-up treatment, details regarding anesthesia use, volume injected, kit numbers, whether needle or cannula was used, characteristics of the procedure (eg, subject assessment of procedural pain), and characteristics of the product (eg, TI evaluation of injection ease and moldability) will be recorded on the eCRF.

Concomitant medications, concurrent procedures, therapies, and AEs will be monitored continuously throughout the study. The procedures and evaluations for the treatment period are listed by visit in [Table 1](#).

For treatment group subjects, routine follow-up visits for safety and effectiveness will occur at Months 1, 3, 6, 9, and 12 after the last treatment (initial or touch-up). The procedures and evaluations for the follow-up period are listed by visit in [Table 2](#).

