## 6.2 Procedures to be Performed

The TIs will be trained in the injection technique, and TIs and EIs will be trained in the use of the AIHS prior to initiating enrollment.

Throughout the study, to the extent possible, it is recommended that treatment and safety assessments for a particular subject be performed by the same TI, and effectiveness assessments (AIHS and Global Aesthetic Improvement Scale [GAIS]) be performed by the same EI. If it is not possible to use the same evaluator to follow the subject, it is recommended that evaluations overlap (examine the subject together and discuss findings) for at least 1 visit.

At each visit and safety telephone call, the TI (or designee) will solicit and record information about adverse events (AEs) and concomitant medications, therapies, and treatments. The TI (or designee) will begin by asking the subject a general, non-directed question, “How have you been feeling since the last visit?” Directed questioning and examination will then be done as appropriate and may include referral to a retinal specialist.

Any subject with any ophthalmic signs and symptoms or vision loss will be referred immediately to a retinal specialist for an examination. All reported AEs will be documented.

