## **11.1 Definitions**

### **11.1.1 Adverse Event**

An AE is defined in accordance with ISO 14155 as “any untoward medical occurrence, unintended disease or injury, or untoward clinical signs (including abnormal laboratory findings) in subjects, users, or other persons, whether or not related to the investigational medical device.” This definition includes events related to the investigational medical device or comparator and events related to the procedures involved except for events in users or other persons, which only include events related to investigational medical devices.

Disease signs and symptoms that existed prior to the study treatment are not considered AEs unless the condition recurs after the subject has recovered from the pre-existing condition or the condition worsens in intensity or frequency during the study.

AEs will be monitored throughout the study beginning with signing of the ICF. At each postscreening visit, the TI (or designee) will begin querying for AEs by asking each subject a general, non-directed questions, “Have you had any changes to your condition since your last visit?” Previous AEs and changes in therapy/concomitant medications are to be updated. Directed questioning and examination will then be done as appropriate. All reportable AEs and clinically significant abnormal laboratory findings will be documented on the appropriate eCRF.

The following is a list of known potential AEs, including those related to visual symptoms:

- Redness, swelling, or a rash, which may be associated with itching, pain on pressure, after the injection
- Pain at injection site

- Bruising
- Nodules or “lumpiness” at the injection site
- Discoloration of the injection site
- Rare cases of allergy, severe sensitivity, localized inflammation and abscesses
- Very occasionally, delayed side effects can occur many months after the treatment. These side effects may appear as red lumps showing up underneath the skin, or intermittent episodes of swelling.
- In rare circumstances, facial fillers have been injected into blood vessels causing blockage and embolization which can result in skin necrosis, ulceration, or vision changes. Risks to vision include complete blindness, partial blindness, blurred vision, double vision, loss of peripheral vision, loss of a portion of the visual field or anterior segment ischemia (characterized by decreased vision and pain). These effects can be temporary or permanent but are rare.

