- Swelling or edema around the eye following an injection can result in a temporary decrease of vision.
- In rare circumstances, facial fillers have been associated with granulomas, which are small inflammatory nodules under the skin.

Unforeseeable risks or results are also a possibility. The risk of developing a serious complication is small. If a complication occurs, subjects will be advised to contact the TI who will use his/her medical judgment to do whatever is necessary to treat the subject. In the event of visual disturbance, the subject must also be referred to a retinal specialist for evaluation and for appropriate care.

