### **11.1.2 Adverse Event of Special Interest**

An AE of special interest (AESI) is defined as any vision-related AE. See [Section 11.3](#) for procedures for reporting an AESI.

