### 11.3 Procedures for Reporting an AE or ADE

All AEs or ADEs occurring during the study period (beginning with signing ICF) are to be recorded on the appropriate eCRF by the TI. Any AE that is ongoing at the exit visit must be followed up as appropriate.

The TI will report AESI interest to Allergan within 24 hours of awareness of the event by completing an AE eCRF and notifying Allergan study management personnel and the Medical Safety Physician by fax or email. Allergan will notify FDA of any AESI within 10 days of Allergan’s awareness of the event.

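### Protocol Section 6.2.3.1 lets an immediate site visit stand in place of retinal referral after a telephone report of vision change, against the mandatory referral in Sections 6.2 and 11.1.1

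*Protocol*

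**What the plan says.** Three places in the protocol tell site staff what to do about eye symptoms.

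- **Section 6.2.3.1** (follow-up after initial treatment) deals with reports made at the telephone follow-up or in an unscheduled call. If vision has changed, "the subject will be asked to come in immediately or will be referred to a retinal specialist for further evaluation". The touch-up, repeat and control-group optional treatments use the same procedures (Sections 6.2.3.1, 6.2.3.2 and 6.2.4.2), so the sentence applies after every treatment.
- **Section 6.2** (introduction to all procedures) covers calls as well as visits: "At each visit and safety telephone call, the TI (or designee) will solicit and record information about adverse events (AEs"). On general adverse-event questioning it is permissive: "Directed questioning and examination will then be done as appropriate and may include referral to a retinal specialist". Its next paragraph is not: "Any subject with any ophthalmic signs and symptoms or vision loss will be referred immediately to a retinal specialist for an examination".
- **Section 11.1.1** closes its list of known risks with "In the event of visual disturbance, the subject must also be referred to a retinal specialist for evaluation and for appropriate care".

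Vision events also have special reporting status. Section 11.1.2 says "An AE of special interest (AESI) is defined as any vision-related AE", and Section 11.3 gives the Treating Investigator 24 hours to notify the sponsor. The SAP's design summary mentions the Day 3 call but gives no instruction on vision symptoms. No redaction touches these sentences.

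**The concern.** The sentence that a staff member handling a call is most likely to look up is the only one of the three that offers an alternative to referral. It carries no cross-reference to Section 6.2 or 11.1.1, and a designee may take the call.

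A site visit is not the same as a retinal examination. The protocol's own vision checks are Snellen acuity, confrontational fields and ocular motility, done by the Treating Investigator or a designee. Section 9.1.2 requires Treating Investigators to practise in aesthetic medicine, plastic, cosmetic or reconstructive surgery, or dermatology; retinal expertise is not asked for. Section 2.2 names retinal artery occlusion as a rare but serious risk in this area, and Section 11.1.1 says that vision effects of embolization may be permanent. Section 11.1.1 also says that swelling can lower vision for a time, which gives staff a benign explanation that could lead them to wait. What is at stake is the speed of specialist care for a rare harm that may not be reversible.

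**Working it through.** The point rests on wording, so there is no figure of the plan to reproduce. The three instructions compare as follows.

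| | Section 6.2.3.1 | Section 6.2 | Section 11.1.1 |
|---|---|---|---|
| Setting | Telephone report | Visits and safety calls | Any |
| Trigger | Change in vision | Ophthalmic signs and symptoms, or vision loss | Visual disturbance |
| Action | Site visit *or* referral | Referral | Referral, on top of contact with the Treating Investigator |
| Timing of referral | None stated | Immediate | None stated |
| Visit accepted instead of referral? | Yes, as written | No | No |

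**Step 1: do the triggers overlap?** They are worded differently, but Section 11.1.1 lists concrete cases: "Risks to vision include complete blindness, partial blindness, blurred vision, double vision, loss of peripheral vision". Blurred or double vision is a change in vision, an ophthalmic symptom and a visual disturbance. One telephone report can therefore trigger all three rules.

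**Step 2: does Section 6.2 reach the telephone call?** Yes. Its text names safety calls, and Section 6.2.3.1 is one of its subsections.

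**Step 3: does the permissive sentence in Section 6.2 soften its rule?** No. That sentence concerns general adverse-event questioning; the mandatory sentence follows it and is specific to the eye.

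**Step 4: apply the rules to a subject who telephones with blurred vision.**
- Under Section 6.2.3.1 alone, asking the subject to come in at once completes the instruction.
- Under Section 6.2, referral is due immediately, at the time of the call.
- Under Section 11.1.1, referral is due whatever else is done.
- In Section 6.2.3.1 the word for immediacy is attached to coming in, so even its referral branch lacks the timing that Section 6.2 requires.

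**Step 5: what happens if the subject comes in?** Sections 6.2 and 11.1.1 then apply at the visit and require referral. Staff who follow only the telephone sentence during the call, but the general rules at the visit, refer late by the time between call and visit. The referral is missed altogether only if the general rules are overlooked at the visit too.

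**Step 6: can all three be met together?** Yes. Immediate referral, with or without a visit, satisfies every sentence. The defect is that the telephone sentence does not tell staff to do this.

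**The case against.** The strongest reply is that nothing is missing. Section 6.2.3.1 sits under Section 6.2, whose rule already covers the call, and the telephone sentence can be read as a first step for a subject who is off site. Whoever comes in meets the mandatory rule on arrival, and the visit itself is to be immediate. Other safeguards exist: vision assessments about 30 minutes after treatment and at Day 14, suspension of treatments at the site if a vascular embolic event leads to vision loss (Section 10.4), and expedited reporting, where "The TI will report AESI interest to Allergan within 24 hours of awareness of the event by completing an AE eCRF".

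Much of this stands. A reader might infer that the protocol waives referral for telephone reports, or that referrals will be missed. The documents support neither: the general duty is intact, and a missed referral would need a second lapse at the visit.

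Two parts do not remove the point. The triage reading is possible, but the sentence does not say that referral follows; it offers the visit as an alternative. The other safeguards do not do the work of a referral either: the scheduled assessments are fixed in time, suspension comes after the harm, and expedited reporting informs the sponsor without sending the subject to a specialist.

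**Conclusion.** The conflict holds as a wording error in a safety instruction and should be fixed. Its likely consequence is a delayed referral; omission is possible but less likely. This rests on two assumptions: that a telephone-reported vision change will usually also be an ophthalmic symptom or visual disturbance, and that some staff may act on the telephone sentence without turning to Section 6.2.

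No size can be given. The documents contain no rate of telephone-reported vision changes or of missed or late referrals. A reader might try to size the point by scheduled Day 3 calls. With 3:1 allocation of 140 subjects, 140 × 3/4 = 105 are treated initially and 35 are controls. The count then runs from 105 (every treatment-group subject has the initial treatment and no optional treatment is taken) to 105 × 3 + 35 × 2 = 385 (all are taken, with no dropout). These are calls, not events, and they do not measure the defect.

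The effectiveness analyses and the special-interest reporting rules are unaffected.

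**What to change.** Replace the telephone sentence in Section 6.2.3.1 with one to this effect: *when a subject reports a vision change in a scheduled or unscheduled call, the site refers the subject to a retinal specialist at once, as Section 6.2 requires; the site may also ask the subject to come in for vision assessments, but that visit neither replaces nor delays the referral.*

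The visit should stay optional. Sections 6.2 and 11.1.1 do not require one, and making it compulsory would add a step and remove the option of sending a subject straight to the specialist. A cross-reference to Section 6.2 alone would be weaker, because the alternative would remain in the text.

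The cost is one sentence in the next protocol amendment. Section 12.2 requires sponsor approval and prior IRB review, since a changed safety instruction is not plainly administrative. A site memo can restate the existing duty in the meantime. There may be a few more referrals for minor symptoms, but Sections 6.2 and 11.1.1 already require those.

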### **6.2.3.2 Repeat Treatment and Follow-up**

Repeat treatment is offered to treatment group subjects who complete the Month 12 visit. If accepted, they will return for repeat treatment within 14 days after the Month 12 follow-up visit.

The order in which the infraorbital hollows are treated will be the same as that for initial treatment. Female subjects of childbearing potential will take a urine pregnancy test; if the test is positive, the subject will not receive repeat treatment and will be exited from the study. The repeat treatment visits and procedures are identical to those for the initial treatment.

Subjects will be followed for 1 month after repeat treatment and will exit the study.

The procedures and evaluations to be performed during repeat treatment and follow-up are listed by visit in [Table 3](#).

### **6.2.4 Control Group**

#### **6.2.4.1 Control Period**

Subjects randomized to the control group will complete a 3-month no-treatment control period with office visits at Months 1 and 3. The procedures and evaluations for the control group during the control period are listed by visit in [Table 4](#).

At the Month 3 visit, subjects will be offered an optional treatment after completion of the Month 3 visit. Control group female subjects of childbearing potential who accept optional treatment will take a urine pregnancy test; if the test is positive, the subject will not receive treatment and will be exited from the study. In addition, the TI (or designee) will perform vision assessments. Control group subjects who decline optional treatment will complete the study after the Month 3 visit. The control period concludes after completion of the Month 3 procedures.

#### **6.2.4.2 Optional Treatment, Touch-up, and Follow-up**

Control group subjects who have optional treatment will be followed for safety only; no effectiveness assessments will be performed.

Female subjects of childbearing potential who accept optional treatment will take a urine pregnancy test; if the test is positive, the subject will not receive treatment and will be exited from the study. In addition, the TI (or designee) will perform vision assessments.

The optional treatment can occur on the same day as the Month 3 visit, after all visit procedures are complete. If the Month 3 visit and optional treatment occur on the same day, all pretreatment study procedures that overlap with the Month 3 procedures do not need to be repeated. If the optional treatment visit occurs after the Month 3 visit, optional treatment must occur within 2 weeks after the Month 3 visit.

The preparation process and performance of procedures after treatment administration will be the same as that described for the initial treatment of the treatment group. Routine follow-up visits for safety will occur at Months 1, 3, 6, and 9 after the last treatment (initial or touch-up). The procedures and evaluations for the optional treatment and follow-up of the control group are listed by visit in [Table 5](#).

### **6.3 Instructions for the Subjects**

During each study visit, subjects will be required to remove all jewelry, make-up, and lipstick, to avoid interference with the digital photographs.

For 10 days before and 3 days after study treatment administration, subjects should avoid using a regimen of anti-coagulation, antiplatelet, or thrombolytic medications; nonsteroidal anti-inflammatory drugs; supplements of Vitamin C or E, garlic, ginkgo biloba, or ginseng; or other supplements known to increase coagulation time. These precautions are recommended to reduce the risk of posttreatment bleeding or bruising.

Within the first 24 hours after treatment, it is recommended that subjects avoid strenuous exercise, extensive sun or heat exposure, and alcoholic beverages. Exposure to any of the above may cause temporary redness, swelling, and/or itching at the injection sites.

For 2 days after treatment, it is recommended that subjects avoid unnecessary external compression of the treatment site that could cause displacement or indentation where the product has been placed.

For 1 week after treatment, subjects will be advised not to have a massage, enter a hot spring or sauna, or go swimming.

For 3 months after treatment, it is recommended that subjects not wear tight-fitting swim goggles.

Subjects will also be instructed to contact the TI or his/her research staff to report any unexpected symptoms or to ask questions about the study.

## 6.4 Unscheduled Visits

An unscheduled visit may occur for safety purposes (eg, if the subject needs to obtain information regarding adverse events or ISRs). An unscheduled visit may also occur to repeat facial digital images if those obtained at the scheduled visit are poor quality images. Applicable procedures will be performed and recorded on the eCRF.

## 6.5 Early Discontinuation of Subjects

Each subject reserves the right to withdraw from the study at any time without jeopardy to his/her future medical care. All follow-up procedures scheduled to be performed at the final site visit should be performed at the subject's last site visit. Subjects may also be administratively withdrawn if they do not return for follow-up visits. For any subject who withdraws from the study, the date and reason for withdrawal will be recorded on the eCRF. If a treatment-related AE is ongoing at the time of withdrawal, the TI will attempt to follow the subject until the AE has been resolved or follow-up is no longer possible. The TI shall ask for the subject's permission to follow his/her status/condition outside the study.

Randomized subjects who withdraw before treatment will not be replaced by another subject. The subject number and associated randomization number of the withdrawn subject should not be reassigned to a different subject.

If a subject fails to return for 1 or more scheduled study visits, the TI (or designee) will attempt to contact the subject to determine and document the reason the subject has failed to return and to encourage compliance with the study visit schedule.

At regular intervals, the TI (or designee) will record on the eCRF the reasons for which any subjects are discontinued from the study, including subjects who signed the ICF but do not proceed to randomization.

## 6.6 Withdrawal Criteria

The subject may withdraw at will at any time for any reason.

If a subject has a positive urine pregnancy test prior to initial treatment, the subject will not be eligible for treatment and will be withdrawn from the study. If a subject has a positive urine pregnancy test after treatment, she will continue all scheduled visit and non-treatment procedures. The pregnancy will be followed as described in [Section 10.3](#).

